1. INTRODUCTION

1.1 Rationale for Proposed Study

Breast density has been found in multiple studies to be the primary factor in mammography failure and to increase the odds of missed breast cancer by nine- to fifteen-fold.¹⁻⁴ While mammography registry studies have reported sensitivities as high as 82% for women with dense breasts,⁵ these studies inflate the sensitivity of mammography by failing to account for tumors that are occult both on the study mammogram and clinically during the study interval. In contrast, studies in which mammography is compared against a supplemental screening technique demonstrate that the sensitivity of mammography in women with dense breasts ranges from only 21% to 50%,⁶⁻¹¹ revealing that mammography misses over half of tumors in dense breasts. The average percent mammographic density decreases with increasing age, which explains why the limitations of mammography are more pronounced in younger women¹²⁻¹⁴: the rate of breast cancer not detected by screening mammography is 15 times as high in women 40 to 49 years of age with breasts that are in the most dense category (extremely dense) vs. the least dense category (almost entirely fatty).⁴

Breast density is also associated with advanced cancer presentation: in a cross-sectional analysis of tumor characteristics in 546 women diagnosed with invasive breast cancer, women with a tumor size >1.0 cm were more likely to have dense breasts compared with women with a tumor size ≤ 1.0 cm after adjusting for confounders.¹⁵ Breast density is also the primary factor associated with the presentation of an interval cancer, defined as breast cancer diagnosed within 12 months of a negative screening mammogram². The odds ratio for an interval cancer is 17.8 for women with mammograms defined as having $\geq 75\%$ density compared to those with $<10\%$ density.¹² When characteristics of interval cancers are compared in women with dense breasts (defined as $\geq 25\%$ density) vs. those with $< 25\%$ density, tumors in dense breasts were more likely to be larger ($P < 0.001$) and have lymph node metastases ($P = 0.001$). However, there were no differences in proliferation rates between interval and screen-detected cancers in dense breasts, suggesting that interval-detected cancers in women with dense breasts are larger not because they are more biologically aggressive, but because of a delay in detection. The hazard ratio for breast-cancer specific mortality was three times higher for interval cancers compared to screen-detected cancers, but this association disappeared in the dense breast group after adjusting for tumor size.¹⁶ This evidence suggests that detecting tumors at a smaller size in women with dense breasts would have a significant mortality benefit.

Breast density legislation has provided an important mechanism of informing women about the implications of breast density in masking cancers on mammography. Most state-mandated breast density letters contain language encouraging women to “use this information to discuss with your health care provider whether other supplemental tests in addition to your mammogram may be

appropriate for you" (Michigan letter). However, the recent update to the United States Preventive Service Task Force guidelines on breast cancer screening failed to provide guidance in making these decisions, stating that "Overall, many important questions remain about the potential role of breast density in individualizing screening approaches, and the current evidence is insufficient to recommend a specific screening strategy for women with increased breast density"¹⁷. According to a recent national survey conducted by our team, almost half of screening-eligible women report that receipt of information about breast density without guidance on decision making would cause anxiety and confusion,¹⁸ underscoring the need for data about relative benefits and harms for the supplemental screening options to inform women and providers.

1.2 Gaps in Evidence for Supplemental Screening

Current evidence for supplemental screening is insufficient for several reasons. First, previous trials have compared supplemental screening options to 2D mammography: now that digital breast tomosynthesis (DBT) is rapidly becoming the standard screening approach, it is important to reassess supplemental screening performance relative to DBT. Second, whole breast ultrasound (WBUS) is becoming the default option for supplemental screening due to its widespread availability and the perception of no risk due to lack of ionizing radiation. However, the limitations of WBUS include a very high false positive rate (>25% reported in some studies) and a modest incremental cancer detection rate (ICDR) of 2 to 4/1000 when compared with a functional supplemental screening test such as MRI.^{8,19,20} Adopting a supplemental anatomic imaging technique, such as ultrasound, to compensate for the limitations of the standard anatomic screening technique, which is soon to be DBT, fails to harness the advantages conferred by a functional imaging technique.

1.3 MRI as a Supplemental Screening Tool

MRI, unlike mammography and ultrasound, is a functional breast imaging tool and has consistently demonstrated the highest yield of cancer detection of any breast imaging modality (Incremental cancer detection rate [ICDR] after negative mammography and WBUS was 14.7/1000 in a U.S. population at increased risk and 11/1000 in an average-risk European population).^{8,21} In another European study, the interval cancer rate after MRI was 0%.¹¹ In a cohort of BRCA carriers, invasive tumor size at diagnosis averaged 0.9 cm in the MRI group (13% node positive), compared with 1.9 cm in the mammography-only group (40% node positive). In the same cohort, serial MRI screening over a mean of 3.2 years reduced the incidence of late-stage disease presentation, from 6.6% in controls to 1.9% in women screened with MRI.²² These findings illustrate that MRI screening reduces the reservoir of advanced and interval cancers left behind by anatomic modalities.

However, multiple barriers exist to implementing MRI beyond the high-risk group. MRI costs up to ten times more than other breast imaging modalities. Technical expertise is required to produce high quality examinations just as advanced radiologist training is required for interpretation to

minimize variability in specificity.²³ It is not known whether these barriers can be overcome by abbreviated MRI, which uses a scan time of less than 10 minutes and thus could potentially reduce cost of the examination. Additional barriers include recall rates as high as 26% in some studies,⁸ potential contra-indications, and concerns about intracranial gadolinium accumulation.²⁴⁻²⁶ These barriers to MRI screening implementation beyond the high-risk group underscore the need to identify more cost effective functional imaging techniques with a lower rate of false positive findings.

1.4 Molecular Breast Imaging as Functional Screening Tool

Molecular Breast Imaging (MBI) is a nuclear medicine technique utilizing a specialized gamma camera optimized for imaging the breast. MBI and MRI are both functional imaging techniques: whereas MRI exploits different vascular properties of tumors relative to normal breast tissue, MBI exploits heightened mitochondrial activity, leading to preferential uptake of ^{99m}Tc-sestamibi in breast tumors, regardless of surrounding breast density. Unlike older-generation scintillating gamma cameras (e.g. scintimammography or breast-specific gamma imaging), MBI employs solid-state cadmium zinc telluride (CZT) detectors in a dual-head configuration, allowing for improved count sensitivity, spatial resolution, energy resolution, and lesion detection, along with an attendant reduction in radiation dose.^{27,28}

In two prospective screening trials performed at Mayo Clinic Rochester by our team involving over 2500 asymptomatic women presenting for screening with dense breasts on previous mammogram, the addition of MBI to 2D digital mammography increased breast cancer detection almost four-fold.^{9,10} In the most recent trial, the ICDR of MBI was 8.8 per 1000. The ICDR was significantly increased for invasive cancers but not DCIS, suggesting that MBI detects clinically important cancers rather than contributing further to overdiagnosis. The majority of cancers detected by MBI were node negative, confirming its role in early detection. MBI also detected node positive and large cancers that were mammographically occult, thus unveiling the reservoir of potentially lethal cancers left undetected by mammography. MBI also demonstrates favorable false positive and biopsy rates relative to screening WBUS and MRI. The addition of MBI to mammography raised the recall rate by 6.6%. MBI is FDA-approved, clinically available at over 50 U.S. sites to date, less expensive than mammography (at our institution), and much less complex to interpret relative to WBUS or MRI.

Efforts by our team over the past decade to improve detector technology and optimize injection and patient preparation procedures have resulted in a low-radiation dose MBI protocol. For the proposed study, 8 mCi (300 MBq) ^{99m}Tc-sestamibi will be used, delivering an effective radiation dose (a metric that considers burden and risk to the entire body) of 2.4 mSv. The dose of MBI combined with DBT (~0.5 mSv) would be 2.9 mSv. This total dose is considered safe for routine

screening use, as it is below the level of natural background radiation (3 to 10 mSv) and consistent with national and international guidelines stating that risks of medical imaging at doses below 50 mSv are “too low to be detectable and may be non-existent”.²⁹⁻³¹ In addition, sestamibi is a commonly-used radiopharmaceutical with an excellent safety profile, with over 30 years of clinical use in cardiac and parathyroid testing.

1.5 Significance of the Study

The significance of this study is that it will be the first prospective trial to compare MBI, a relatively low-cost functional breast imaging technique, to DBT, the new standard anatomic breast cancer screening technique in women with dense breasts. This study is also the first to evaluate two consecutive annual MBI scans to assess change in advanced cancer presentation after introduction of a functional imaging technique. These data will inform individualized decisions on supplemental screening and determine if a functional technique that is relatively low in cost and complexity of interpretation can eliminate the reservoir of clinically important breast cancers that remain occult on anatomic techniques. This study will also provide exploratory data about the optimal frequency of repeat MBI.

2. STUDY OBJECTIVES

2.1 Primary Endpoint

The primary aim for this study is to compare the **rate of detection of invasive cancers** between DBT alone vs. the combination of DBT with supplemental MBI at Year 1 screening.

2.2 Secondary Endpoints

Secondary Endpoints include the following:

1. To compare the invasive cancer detection rates of DBT alone vs. MBI alone at Year 1 screening.
2. To compare the screening performance metrics of sensitivity, specificity, recall rate, biopsy rate, positive predictive value and negative predictive value for DBT and MBI.
3. To compare tumor characteristics of all cancers (invasive and noninvasive) detected on DBT and MBI, including size, nodal status, and molecular subtype.
4. To assess the reduction in advanced cancer rate with incorporation of MBI screening by comparing advanced cancer rate observed at Year 2 screening relative to that at Year 1.
5. To assess the rate of interval cancers with incorporation of MBI screening.
6. To examine the relative performance of DBT and MBI within subgroups categorized by breast cancer risk.

3. SELECTION OF PATIENTS

Potentially eligible patients who are scheduled for a screening DBT will be prescreened based on their breast density on most recent prior mammography examination. Potentially eligible patients

will be contacted by letter or telephone to assess eligibility and to offer enrollment if eligible. Study patients will be enrolled in this study for up to 30 months.

3.1 Inclusion Criteria

1. Patient is a consenting female age 40-75 years.
2. Patient is scheduled for routine screening DBT.
3. Patient is asymptomatic for breast disease.
4. Patient had heterogeneously dense or extremely dense breasts on most recent prior mammography examination (BI-RADS c or d) within 24 months of enrollment.
5. Patient is able to participate fully in all aspects of the study (completing study visits and study data collection).
6. Patient understands and signs the study informed consent.
7. Patient anticipates being able to return one year after study enrollment to complete the second round of screening.

3.2 Exclusion criteria

1. Patient is currently pregnant or plans to become pregnant during the course of the study.
2. Patient is currently lactating.
3. Patient has had a prior MBI.
4. Patient has had a prior whole breast ultrasound (WBUS) for screening, with either a hand-held ultrasound probe or automated system, within 12 months prior to study enrollment.
5. Patient has had a prior breast MRI.
6. Patient has had a prior contrast-enhanced mammogram (CESM or CEDM).
7. Patient is concurrently participating in any other breast imaging research studies that involve undergoing additional breast imaging tests beyond routine screening with mammography, including but not limited to contrast-enhanced mammography, WBUS, MBI, or contrast-enhanced breast MRI.
8. Patient has had a breast biopsy within 3 months prior to study enrollment.
9. Patient has had breast surgery within 12 months prior to study enrollment.
10. Patient is currently undergoing treatment for breast cancer or planning surgery for a high-risk breast lesion (ADH, ALH, LCIS, papilloma, radial scar).
11. Patient is currently taking a chemoprevention agent for breast cancer risk reduction or osteoporosis prevention (tamoxifen, raloxifene, anastrazole, letrozole, exemestane).
12. Patient has a known history of any condition or factor judged by the investigator to preclude participation in the study or which might hinder study adherence.

4. STUDY DESIGN

A total of 3006 participants will be enrolled in this study across multiple sites. This study will directly compare the results from two clinical procedures, Digital Breast Tomosynthesis (DBT) and Molecular Breast Imaging (MBI). After enrollment, study participation involves 2 study visits for breast screening – one at the beginning of the study and a second visit one year later. Participants will be enrolled in the study for up to 2.5 years (30 months) to ascertain breast cancer status, and may be contacted at the end of study if breast cancer status cannot be ascertained based on chart review, alone. Study schema is provided in Figure 1 and study schedule in Table 1.

Figure 1: Study Schema

[figure not shown]

Table 1: Study Schedule

	Pre-Screening	Enrollment	Study Visit 1 ^{1,2}	Study Visit 2 ²
Telephone Prescreen Eligibility	X			
Inclusion/Exclusion Criteria		X		
Informed Consent		X		
Medications		X		X
Demographics		X		
Breast Health History and Risk Assessment Survey ⁴		X		
Abbreviated Breast Health History and Risk Assessment Survey ⁴				X
Urine Pregnancy Test (if necessary)			X	X
DBT and MBI Exams ³			X	X ⁵

¹Enrollment and study visit can be completed in one visit or over the course of two visits.

²Study Visits can be completed within 3 business days.

³DBT and MBI exams are targeted to be performed on the same day if possible and required to be completed within three business days of each other prior to initiation of any diagnostic workup.

⁴In order to minimize the amount of time participants will spend at this visit; they will be given the option of having the breast health history and risk assessment survey e-mailed to them. If participants choose this option; they will need to have this survey completed and submitted prior to study visit 1. If not, they will be asked to complete the survey while in-person prior to their radiology imaging.

⁵Should be targeted for 335 to 455 days from Year 1 MBI screening.

5. IMAGING

5.1 Imaging Procedures

At Year 1 screening, all patients will undergo both DBT and MBI targeted to be performed on the same day if possible and required to be completed within three business days of each other prior to initiation of any diagnostic workup. All patients who did not receive a diagnosis of breast cancer during Year 1 will undergo subsequent annual MBI targeted to be performed at approximately one year (Year 2 screening) after Year 1 screening; and should be targeted for 335 to 455 days from Year 1 MBI screening. The Year 2 MBI should be scheduled within 3 business days of the Year 2 DBT if possible; completion of Year 2 DBT is encouraged but not required.

5.1.1 DBT Procedure

DBT technique will be defined as per standard of care, which may include CC and MLO tomosynthesis views with either a 2D full field digital mammogram or synthetic 2D views.

5.1.2 MBI Procedure

1. **Equipment** – MBI examinations will be performed on FDA-approved direct conversion dual-head cadmium zinc telluride gamma camera systems (Discovery NM 750b, GE Healthcare, or LumaGem, CMR Naviscan).
2. **Technologist** – Nuclear medicine technologists will perform radiotracer injections.
3. **Patient preparation** – Patients will be asked to fast for a minimum of 3 hours prior to the MBI examination, when possible, as prior studies have shown fasting to improve uptake of Tc-99m sestamibi in breast tissue by reducing splanchnic and hepatic blood flow.³² Patients may take fluids, including black coffee, tea, diet soda and water. Patients will remove all clothing and jewelry above the waist and put on a patient gown. Patients may be given a warm blanket to wrap around their shoulders and chest for approximately 15 minutes prior to the Tc-99m sestamibi injection, in order to increase peripheral blood flow to breast tissue and thus improve Tc-99m sestamibi uptake.
4. **Tc-99m sestamibi injection** – The technologist should verify that the patient is not pregnant or breast feeding prior to injection of Tc-99m sestamibi. A Nuclear Medicine technologist will deliver an intravenous injection of the Tc-99m sestamibi dose in an antecubital vein of either arm. The target administered activity will be 8 mCi (300 MBq) Tc-99m sestamibi. Residual activity after injection should be measured and decay-corrected to calculate the actual administered activity for each MBI examination. The requested dispensed activity of Tc-99m sestamibi to achieve an approximate administered activity of 8 mCi will depend on site-specific standard of care. Infiltration or extravasation of the injected dose into the soft tissue rarely occurs (~1-2% of studies). If infiltration is suspected, the technologist will observe the count rate obtained on a persistence view prior to beginning imaging. If the count rate is lower than typical (defined as less than 0.2 kcts/minute in the CC view and less than 0.3 kCts/minute in the MLO view for an average-sized breast) the technologist will image the injection site to evaluate. If there is no evidence of infiltration on imaging of the injection site, the technologist will proceed with the breast images. If infiltration is confirmed by both low count rates and high uptake at the injection site, the technologist will ask for the patient's consent to proceed with a second injection of 8 mCi Tc-99m sestamibi. The patient will be given the option to refuse a second dose and continue with the study, although poor image quality may be obtained, or to discontinue MBI imaging and thus end study participation.
5. **Image Acquisition** - MBI imaging will commence immediately after injection. Two views of each breast will be acquired in the cranio-caudal and mediolateral oblique projections.

Acquisition duration will be 10 minutes per view. Images will be acquired using an energy acceptance window of 110-154 keV. For each view, patients will be seated with the breast positioned between the two detectors. The persistence-scope should be used to validate correct breast positioning. If available, the recent mammogram can be viewed to replicate positioning on the MBI. Light compression is applied to stabilize the breast and to limit motion artifact. Placement of pillows behind the patient's back is recommended to reduce motion and increase comfort. Verification of the patient's comfort level and ability to complete 10 minutes of imaging in the position should be done before acquisition begins. Compression thickness for each MBI view will be recorded. In participants with breasts larger than the detector field of view, the technologist may opt to acquire two 10-minute tiled MLO views of each breast, in place of a CC and MLO view, in order to ensure that the entire breast is included in the image set. During the acquisition of each view, the technologist will briefly place the appropriate Co-57 laterality markers (R for right and L for left) in the field of view until well seen on the persistence screen. The patient will be visually monitored by the nuclear medicine technologist from the time of injection of the radionuclide until image acquisition is completed.

6. Post-acquisition processing – Following completion of the acquisition, the technologist will format the acquired images in the standard format used for MBI display and interpretation, showing 8 images collected from bilateral CC and MLO positions from each of two detector heads.

5.2 Imaging Interpretation

DBT and MBI screening studies will be interpreted by two different radiologists, each blinded to the other modality. The interpreting radiologist may refer to any other breast imaging and breast clinical information from previous years while interpreting the DBT or MBI. At both Year 1 and Year 2 screening, the radiologist will only be blinded to results and images from the other screening test (DBT or MBI) performed within 3 business days as part of the study protocol. Interpretations will be recorded independently for both DBT and MBI. Following independent interpretation, if either exam received a positive interpretation, then the breast radiologist who interpreted the MBI will perform an integrated assessment.

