8.4 Definition of Analysis Set

The Analysis Set for each screening year will be defined as the subset of enrolled patients who met eligibility criteria and completed screening imaging with both DBT and MBI.

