8.6 Secondary Endpoints

- 1. To compare the rate of detection of invasive cancers between DBT alone vs. MBI alone at Year 1 screening.**

The comparison will be based on a 2-sided McNemar's test at statistical significance level alpha= 0.05.

2. To compare the screening performance metrics of sensitivity, specificity, recall rate, biopsy rate, positive predictive value and negative predictive value for DBT and MBI.

For both years of the study imaging (Year 1 and Year 2), the following secondary endpoints will be analyzed to compare performance of

- DBT alone vs. MBI alone, and
- DBT alone vs. the combination of DBT with supplemental MBI.

Sensitivity will be estimated for each modality as the proportion of women with breast cancer who have true positive test results. **Specificity** will be estimated as the proportion of women without breast cancer who have TN test results. Uncertainty in the estimate of sensitivity will be quantified through a two-sided 95% confidence interval (CI) based on the binomial distribution. If a sufficient number of radiologists interpret exams from multiple patients with breast cancer, secondary analysis may also include a 95% CI and chi-squared test adjusted for clustering of results within radiologist to allow generalization to both the population of patients and the population of radiologists.³⁶ For comparisons of DBT alone vs. the combination of DBT with supplemental MBI, a structural zero results due to the paired nature of the data and direct comparisons cannot be tested under a null hypothesis of equivalence. Analysis will alternatively focus on the conditional diagnostic odds ratio (cDOR) to quantify the added value of MBI over DBT alone.

Recall rate (defined as the proportion of patients recalled from the screening test for diagnostic workup among the total number of patients screened), and **biopsy rate** (defined as the proportion of patients in whom biopsy is generated from a particular modality among the total number of patients screened) will be estimated employing analytical strategies similar to sensitivity and specificity. McNemar's test will be used to compare rates between two modalities.

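### Year 2 DBT and MBI pairs done more than 3 business days apart have no guaranteed blind, yet can enter the Year 2 paired performance comparisons

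*Combined protocol and SAP*

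**What the plan says.** Section 5.2 opens with a general rule: "DBT and MBI screening studies will be interpreted by two different radiologists, each blinded to the other modality". It then lets a reader use earlier material: the reader "may refer to any other breast imaging and breast clinical information from previous years while interpreting the DBT or MBI". Next it defines the reach of the blind at both Year 1 and Year 2: "the radiologist will only be blinded to results and images from the other screening test (DBT or MBI) performed within 3 business days".

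On spacing, section 5.1 makes the 3-day limit mandatory at Year 1. For Year 2 it says: "The Year 2 MBI should be scheduled within 3 business days of the Year 2 DBT if possible; completion of Year 2 DBT is encouraged". Year 2 DBT is thus optional. Table 1 footnote 3 in section 4 is attached to the row for the DBT and MBI exams at both visits. It says that the tests are "required to be completed within three business days of each other prior to initiation of any diagnostic workup", with no exception for Year 2.

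On analysis, section 8.4 defines the Analysis Set for each screening year as eligible patients who "completed screening imaging with both DBT and MBI". Section 8.6 item 2 plans two contrasts for Year 1 and for Year 2: DBT alone against MBI alone, and DBT alone against DBT with MBI. The metrics are sensitivity, specificity, recall rate, biopsy rate and predictive values.

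**The concern.** A paired accuracy comparison treats the two readings of one woman as separate judgements. A reader who knows the other result tends to agree with it. That removes discordant pairs, which are the information a paired test uses, and it can credit one modality with a lesion that the other revealed.

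The direction of the bias depends on which test is read second, and the plan does not fix the order. If DBT is read second with MBI known, DBT can gain cancers that MBI found, so the increment from MBI is understated in both contrasts. If MBI is read second with DBT known, MBI alone looks closer to DBT than it is.

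The exposed results are the Year 2 part of secondary endpoint 2. They rest on few cancers, so a handful of altered calls could change how they read.

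**Working it through.** **1. Chain of provisions at Year 2**

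| Question | Section | Answer |
|---|---|---|
| What is the reader blinded to? | 5.2, specific sentence | Only the other test done within 3 business days |
| Must the Year 2 tests fall in that interval? | 5.1 | No, preferred only |
| | Table 1, footnote 3 | Yes (conflicts with 5.1) |
| Are pairs outside it excluded? | 8.4 | No; completing both tests is enough |
| Are they used in paired comparisons? | 8.6 item 2 | Yes, both contrasts |

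No section excludes, flags or separately analyses Year 2 pairs outside the interval.

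**2. What is not exposed**

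Section 8.5 (primary) and section 8.6 item 1 concern Year 1 only, where 5.1 requires the interval. The sample size in 8.7 is for that Year 1 primary endpoint, and it reproduces. For a one-sided exact binomial test with null 0.001, alternative 0.004 and alpha 0.025 at n = 2631, the rule is 7 or more additional detections, with exact alpha 0.0181 and power 0.9001. At n = 2630 the power is 0.8998. Adding 375 gives 3006. Nothing here changes those figures.

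**3. Size at Year 2 (assumptions only)**

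The documents give neither the number of Year 2 cancers nor the share of pairs outside the interval.

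- Weight of one cancer in a sensitivity estimate = 1 / number of cancers. For an assumed 10 to 25 cancers this is 1/25 = 4 to 1/10 = 10 percentage points.
- Pairs outside the interval = 2631 × share, using 2631 as a convenient denominator. Shares of 1%, 5%, 10% and 20% give about 26, 132, 263 and 526 pairs.
- Cancers in such pairs = 2631 × cancer rate × share. At 5 per 1000 and 5%: 2631 × 0.005 × 0.05 = 0.7. At 10 per 1000 and 20%: 2631 × 0.010 × 0.20 = 5.3.
- Fragility of a paired test on few cancers, for illustration: an exact McNemar split of 10 against 2 gives p = 2 × (1 + 12 + 66)/4096 = 0.039. If one discordant cancer becomes concordant, 9 against 2 gives p = 2 × (1 + 11 + 55)/2048 = 0.065.

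**The case against.** The best reply is that section 5.2 already blinds both readers. Its opening sentence has no time limit, and the only other imaging it lets readers consult is from previous years, which a same-year test is not. On this reading the 3-day phrase merely describes the usual pair. Section 5.3 adds that work-up imaging waits until both blinded interpretations are complete, with no restriction to Year 1.

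Part of this stands. A reader might infer that unblinded reads do enter the analysis. The text shows only that they can, because the specific sentence limits the blind while the general one does not. A reader might also infer that the second radiologist would see the work-up from the first test. Section 5.3 as written is against that, though it sets no Year 2 interval and does not itself extend the blind. If work-up did go ahead and found a cancer, section 7 requires no further study imaging. A woman who then skipped the second test would be outside the Year 2 Analysis Set.

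Nor does the 335 to 455 day range imply gaps of up to 120 days between DBT and MBI. It is the target time from the Year 1 MBI, and the documents give no expected spacing within a pair beyond the 3-day target.

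What the reply does not do is settle how a same-year test outside the interval is handled. The two sentences in 5.2 differ in reach, and footnote 3 contradicts 5.1 instead of closing the gap.

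**Conclusion.** The point holds as a gap in the plan, limited to the Year 2 comparisons of secondary endpoint 2, in both contrasts. Followed as written, the plan lets pairs without a guaranteed blind be analysed as separate reads.

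The size of the bias cannot be estimated, because the share of such pairs is unknown. The 4 to 10 percentage points rest on an assumed 10 to 25 Year 2 cancers and apply to each cancer call that unblinding changes. A reader might take them as the effect of every unblinded cancer pair. That would be wrong, since a cancer that the second reader would have called, or missed, either way moves nothing.

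This should be corrected, but it does not threaten the trial's main conclusion.

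**What to change.** Reconcile Table 1 footnote 3 and sections 5.1, 5.2 and 5.3 so that they agree on Year 2 spacing and on what each reader may see. Then do one of the following:

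- State in 5.2 that the blind applies to the same-year paired test whatever the interval. This has to be worded together with 5.3, which ties work-up to completion of both reads.
- Base the main Year 2 paired comparisons in 8.6 item 2 on pairs done within 3 business days. Show all completed pairs as a sensitivity analysis and report the number outside the interval.

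The second option is a change of SAP wording and needs only exam dates, which the reference-standard definitions in section 8 already call for. A stricter condition, that both reads were recorded before either was disclosed, would need read and disclosure times. The documents do not say that these are captured. The cost is somewhat fewer Year 2 pairs in the main comparison. Year 1 analyses and the sample size stay as they are.
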